2.2 Primary Endpoint

The primary endpoint for this study is wound healing (Group 2), as defined by the percent change in wound surface area (surface area is calculated in cm²) from baseline through the active treatment period. Specifically, wound care subjects will have the study device applied at baseline then re-applied two times per week for up to 4 weeks from the start of the active treatment period. Device reapplication will change to weekly when the principal or sub-investigator determines it is permissible or when a maximum of 4 weeks of treatment is reached. Device re-application will continue weekly until the wound is judged to be healed by the wound care practitioner or up to 3 months, whichever comes first. If after 2 consecutive months of treatment with the study device the wound does not exhibit healing, evidenced by a decrease in surface area (cm²), the subject will be returned to standard and established techniques of treatment consistent with the wound etiology.

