2.3 Secondary Objective (Group 2 only)

Group 2 (Efficacy): Wound Care Subjects. The secondary endpoint of the study is to determine if the study device is equivalent to standard and established techniques (standard techniques demonstrate 50% wound healing at 2 months) in subjects with active wounds.

[figure not shown]
IRB# 1331496 Page 17 Version 6.0

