3.2 Subject Population and Sites

Group 1: Initial subjects will be limited to healthy volunteers with intact skin on their lower extremities. Five (5) white subjects and 5 black or African American subjects will be enrolled to evaluate skin differences. Group 1 (healthy volunteers without wounds) will have all follow-up completed and the results assessed before the investigators initiate prior to proceeding to Group 2 (wound care subjects).

Group 2: The subsequent wound care subject study will include 10 subjects from the patient population treated at the OhioHealth Riverside Methodist Hospital Critical Limb Care Center for lower extremity ulceration attributed to diabetes and/or arterial insufficiency.

[figure not shown]

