9.0 STATISTICAL CONSIDERATIONS

Primary Objective.

Group 1 (Safety): Healthy Volunteers. The initial phase of the study is designed to determine the safety of the study device in normal healthy volunteers without wounds. If there are no issues with tolerance, side effects, and/or adverse reactions in normal healthy volunteers, the second phase of the study will proceed with active wound care subjects.

Group 2 (Efficacy): Wound Care Subjects. The second phase of the study is designed to determine the effectiveness of the study device in wound healing in subjects with active wounds (see Primary Endpoint below), and to determine if the study device is equivalent to standard and established techniques (standard techniques demonstrate 50% wound healing at 2 months).

Primary Endpoint.

The primary endpoint for this study is wound healing (Group 2), as defined by the percent change in wound surface area (surface area is calculated in cm²) from baseline through the active treatment period. Wound care subjects will have the study device applied (and re-applied weekly) until the wound is judged to be healed by the wound care practitioner, for up to 3 months total duration. If after 2 consecutive months of treatment with the study device the wound does not exhibit at least 50% improvement in surface area (cm²), the subject will be returned to standard and established techniques consistent with the wound etiology. We will also determine if the study device is equivalent to standard and established techniques (standard techniques demonstrate 50% wound healing at 2 months).

Statistical Analysis Plan.

Descriptive statistics will comprise the bulk of the statistical analysis. Continuous variables will be reported as means and standard deviations, along with median and minimum/maximum values and compared between baseline and follow-up times using paired t-tests and/ or repeated measures ANOVA. Dichotomous and categorical variables will be reported as frequencies with percentages and compared between follow-up times using Chi-square tests or Kruskal Wallis tests. Imputation techniques will be used to account for missing data. Statistical significance will be set at p<0.05 for all the tests.

IRB# 1331496 Page 41 Version 6.0

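### Section 9.0 fixes no comparison time and no handling of outcome-driven exits, so later tests can rest on a selected sample and any of up to 16 treatment visits may be tested at 0.05

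*Combined protocol and SAP*

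**What the plan says.** **Analysis.** Section 9.0 has continuous variables "compared between baseline and follow-up times using paired t-tests and/ or repeated measures ANOVA". It adds: "Statistical significance will be set at p<0.05 for all the tests". On missing data there is one sentence: "Imputation techniques will be used to account for missing data". On emphasis it says: "Descriptive statistics will comprise the bulk of the statistical analysis". It names no primary test, comparison time, multiplicity rule, sphericity correction or imputation method.

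**Endpoint and size.** Section 2.2 defines the primary endpoint as "percent change in wound surface area (surface area is calculated in cm²) from baseline through the active treatment period", without a fixed assessment time. Section 3.2 sets the size of Group 2: "The subsequent wound care subject study will include 10 subjects from the patient population treated". There is no control arm.

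**Who stays under observation (sections 5.9 and 5.11).**
- Healed: device application stops and quarterly follow-up visits, with wound measurements, begin.
- No decrease in area at the 8-week visit: return to standard care, and study follow-up ends.
- Less than a 50% decrease at 12 weeks: the same.
- Two consecutive missed treatment visits: removed and not replaced.

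**Two internal conflicts.** Section 2.3 makes the comparison with standard techniques secondary: "The secondary endpoint of the study is to determine if the study device is equivalent". Section 9.0 carries it under the primary objective and primary endpoint: "We will also determine if the study device is equivalent to standard and established techniques". The Protocol Summary also lists it beside the main Group 2 objective. Separately, the 2-month stopping rule in section 9.0 (less than 50% improvement) differs from the one in sections 2.2, 3.3, 5.1 and 5.11 (no decrease).

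**The concern.** A test of baseline against a later visit estimates the average change only if the subjects measured at that visit represent all who were treated. Here the exit rules act on wound area, which is the variable being tested. After week 8 the non-responders have left and healed wounds are no longer measured at treatment visits. Standard repeated-measures ANOVA needs every subject at every included time. Without a stated method it could therefore drop every early exit, at either end of the outcome range.

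A second problem is independent of the first. The comparison times are left open and each test uses 0.05, so nothing in the text says which p-value counts. With 10 subjects and no control arm, a single significant visit could be reported as evidence of efficacy.

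**Working it through.** **Nothing to reproduce.** The plan gives no power, sample-size derivation or overall error rate. Its only figure is 0.05 per test, taken here as two-sided.

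**Step 1: number of possible tests.** The footnotes to the Group 2 schedule in section 5.1 allow 2 × 4 = 8 visits in weeks 1–4 and 8 in weeks 5–12, so at most 16 treatment visits. It is a maximum because investigators may switch to weekly changes early. Four quarterly visits bring the total to 20.

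**Step 2: selection that follows from the text alone.** A subject who completes treatment enters quarterly follow-up only if healed or with at least a 50% decrease at week 12. Apart from anyone who stopped for an adverse reaction or by choice and stayed on, a baseline-to-follow-up test there is run on responders. If section 9.0's 2-month rule were the one applied, weeks 9–12 would be limited in the same way.

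**Step 3: size of the selection effect.** The documents give no SD, correlation or spread of healing rates, so these are assumptions. The model is log area relative to baseline, with a random slope per subject (SD 0.05–0.25 per week, mean 0) and residual SD 0.15. A wound counts as healed below 5% of baseline. Settings are n = 10, the 16 visit times, 20,000 runs per row and no imputation. Healed subjects leave, and subjects with no decrease at week 8 leave after that visit.

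| Slope SD | Subjects left at week 12 | Week-12 test, all 10 | Week-12 test, those left | Mean log ratio, those left |
|---|---|---|---|---|
| 0.05 | 4.99 | 5.1% | 41.7% | −0.464 |
| 0.10 | 4.95 | 5.2% | 53.7% | −0.925 |
| 0.15 | 4.63 | 4.9% | 54.4% | −1.228 |
| 0.25 | 3.61 | 5.1% | 42.6% | −1.452 |

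Every rejection in the fourth column favours the device. The true mean log ratio is 0. The apparent reduction runs from 1 − exp(−0.464) = 37% to 1 − exp(−1.452) = 77% (geometric means). The Monte Carlo standard error at 41.7% is √(0.417 × 0.583 / 20,000) = 0.35 points, and I quote the range as about 41–54%.

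**Step 4: the direction can reverse.** With a mean decline of 0.2 per week and slope SD 0.15, 37% of wounds heal and 9% fail. The week-12 mean log ratio is −1.82 in those still on treatment and −2.40 in all subjects. That is 1 − exp(−1.82) = 84% against 1 − exp(−2.40) = 91%, so dropping healed wounds now understates the effect.

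**Step 5: multiplicity alone, complete data.** For k independent tests the chance of at least one false positive is 1 − 0.95^k: 18.5% for k = 4, 56.0% for k = 16 and 64.2% for k = 20. Visits within a subject are correlated, so simulation is the better guide for 16 tests on n = 10:
- compound symmetry: 39–40%;
- autoregressive: 30–34%;
- random walk: 27–30%;
- the random-slope model of step 3: 16–30%.

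The overall range is about 16–40%.

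**Step 6: repeated-measures ANOVA, complete data.** With 17 times and n = 10, the uncorrected F test rejects a true null 13–18% of the time. With the Greenhouse-Geisser correction this is 3.5–5.3%.

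**Step 7: one week-8 test.** Subjects with no decrease leave at the week-8 visit, so they are measured there. A single week-8 comparison including all 10 subjects holds its error at about 5%.

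**The case against.** The strongest reply is that this is a 10-subject, first-in-human, single-arm study whose analysis is declared mainly descriptive, and that the plan commits to none of the harmful choices. Much of that stands. Several stronger readings are tempting, and the documents do not support them:

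- **That every visit will be tested.** Section 9.0 says only follow-up times, with paired tests and/or ANOVA. Sixteen tests is the most the schedule allows, not a stated plan.
- **That only subjects still under treatment will be analysed.** The plan promises imputation. What it lacks is a method, and a statement on whether a healed wound is missing or 0 cm². Section 5.11 also allows record-based data collection for some subjects who withdraw or are lost.
- **That observation ends at healing.** It moves to quarterly visits with measurements. It is the non-responders who lose study follow-up.
- **That the exits cause the multiplicity, or that bias always favours the device.** Steps 4 and 5 show otherwise.
- **That a week-8 mean must be overstated.** Subjects with no decrease are measured at week 8. A large distortion there needs a requirement for complete visits through week 12 and no imputation.
- **That the primary endpoint is undecided.** The Summary, section 2.2 and section 9.0 all name percent change in area. Only the rank of the equivalence question varies.

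What the reply does not remove is that p-values are planned, and that an unnamed imputation method is no safeguard when missingness is driven by the outcome.

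**Conclusion.** The concern holds in this limited form. Section 9.0 leaves open which times are tested, which test is primary, and how healed, stopped and removed subjects are scored, while section 5.11 makes presence after week 8 depend on wound area. That permits an outcome-selected analysis. In the no-imputation case it raises the error of a single week-12 test from 5% to about 41–54%, with bias the other way when healing is common. Multiplicity is a separate problem, at roughly 16–40% if all 16 treatment visits were tested.

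These sizes rest on assumed slope SD, residual SD, correlation and healing threshold, and on a log-area model. With no true mean change, the selection effect favoured the device at every slope SD tried. They show what the wording allows, not what the sponsor will do. The responder-only make-up of the quarterly visits needs no such assumptions.

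**What to change.** 1. Name one primary test: percent change in area from Day 0 to the week-8 visit, in all treated subjects, with healed wounds scored 0 cm². State the rule for subjects removed before week 8 (missed visits, adverse reactions, withdrawal). Week 8 is already scheduled, matches the 2-month secondary endpoint, and comes before any exit for non-response.
2. Report all other visits descriptively, without p-values, showing how many subjects contribute and why the others do not.
3. If a trajectory is wanted, replace repeated-measures ANOVA with a mixed model with subject random effects on all available visits, carrying healed wounds as 0 cm². Without that scoring the model does not solve the healed-wound problem. The analysis scale must admit zeros, so plain log area will not do.
4. Replace the imputation sentence with the rules in items 1 and 3.
5. Place the 50%-at-2-months question as secondary in the Protocol Summary and section 9.0, as in sections 2.3 and 2.4.
6. Reconcile the 2-month stopping rule in section 9.0 with sections 2.2, 3.3, 5.1 and 5.11. Which rule is right is for the sponsor and investigators.

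The cost is text changes and fewer p-values. No new visits, subjects or data are needed.

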5.0 STUDY PROCEDURES AND ASSESSMENTS

5.1 Schedule of Events

Group 1 (Healthy Volunteers):

The initial healthy volunteer safety study will last a total of 4.5 weeks. Healthy volunteers will have the study device applied for 3 consecutive days (up to 72 hours), followed by weekly visits for 4 weeks of observation for tolerance, side effects, and adverse reactions. Weekly visits will occur every 7 ± 2 days after the Day 3 visit.

Assessment	Screening (via phone)	Baseline	tion: Day 0Study Device	3 ± 0 days Treatment:	$y 7 \pm 2 \text{ days}^4 \text{ Follow-Up}$:	Unscheduled Visit
Informed Consent		X				
Medical history	X					
Concomitant medications	X	X	X	X	X	X
OhioHealth Research Institute Clinic Visit (Research Only)		X				
Critical Limb Care Center (Riverside Methodist Hospital Wound Center) visit (research-only)			X	X	X	
Shaving of left posterior calf		X				
Photograph			X	\mathbf{x}^5	X	
Noxsano Bandage application			X			
SAR Questionnaire			X	X	X	

Group 2 (Wound Care Subjects):

The wound care subject treatment period will consist of twice per week study device applications to a specific ulceration for up to the first 4 weeks of treatment and then weekly re-application thereafter. When deemed permissible by the clinical judgment of the principal or sub-investigator or when 4 weeks is reached, re-application of the study device will change to weekly. This weekly re-application will occur until the wound is healed, or for up to 12 weeks (whichever occurs first). For subjects that do not exhibit any reduction in wound size at 2 months, application will stop and standard treatment protocols will be pursued.

At the conclusion of the treatment period (maximum of 3 months), subjects will be followed every 3 months for 12 consecutive months for observation of late side effects or adverse reactions (up to 3 months of active treatment, 12 months of follow-up observation, 15 months maximum).

IRB# 1331496 Page 24 Version 6.0

⁴ Day 10, 17, 24, and 31

⁵ Photograph and compensation are given on Day 3 only during Treatment Period

Assessment	Screening / Baseline	Day OInitial Study Device	ery 3 ± 2 days ⁶ Treatment:	$2 \text{ try } 7 \pm 2 \text{ days}^7 \text{ Treatment:}$	$imo \pm 14 days^8 Follow-Up$:	Unscheduled Visit
Informed Consent	X					
Routine medical history / physical exam	X					X
Concomitant medications	X	X	X	X	X	X
HgbA1c (subjects with diabetes)	X					
ABI (subjects with arterial insufficiency)	X					

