5.3 Photographs

Photographs of the study device application site and wounds (Group 2) will be taken using a digital camera, an FDA Class 1 510(k) exempt medical device. Digital photographs are routinely taken in the OhioHealth Riverside Methodist Hospital Critical Limb Care Center, therefore, their equipment will be utilized for the study.

Group 1(Healthy Volunteers): A photograph will be taken on Day 0 of the shaved area on the left posterior calf prior to study device placement. A photograph of the site where the study device was applied will also be taken on Day 3, following removal of the study device, and at each follow-up visit (Days 10, 17, 24, and 31). All photographs will be

IRB# 1331496 Page 25 Version 6.0

⁶ Weeks 1-4, 2 times per week study device changes or until change to weekly is permitted by investigator.

⁷ Weeks 5-12, weekly study device changes until wound has healed or 3 months is reached.

^{83, 6, 9,} and 12 months post-treatment

uploaded into the study electronic case report forms (eCRFs) by a member of the study staff.

Group 2 (Wound Care Subjects): Photographs of the wound with a conventional ruler in place will be obtained at baseline, Day 0 (Initial Device Application), treatment, and follow-up visits. Photographs will be taken by a wound care nurse and uploaded in the study eCRFs by a member of the study staff.

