5.7 Initial Study Device Application Visit

The device sizes available are small $(4 \times 4 \text{ cm})$, medium $(6 \times 6 \text{ cm})$, and large $(6 \times 8 \text{ cm})$, and are all 1-2 cm in thickness (1 cm) at the ends and 2 cm in the center, i.e., the location of the battery). The size used will depend on the size and shape of the wound to be treated (the device must cover the entire area of the wound) and could vary over time. Healthy volunteers will all receive the small $(4 \times 4 \text{ cm})$ device size.

IRB# 1331496 Page 26 Version 6.0

All subjects will be given a Noxsano Bandage Information Sheet (App. G), which will reiterate conversations from the Informed Consent process, including, but not limited to the following:

- ♦ "Troubleshooting" the Noxsano Bandage, including device malfunctions and frequently asked questions;
- ♦ Reporting safety issues, side effects, and adverse reactions.

Group 1 (Healthy Volunteers): A photograph will be taken on Day 0 of the shaved area where the device will be place prior to study device application. The study device will be applied by the Principal Investigator or delegated Sub-Investigator to the shaved area of skin on the left posterior calf. The study device will not be changed over the 3-day treatment period in order to complete an uninterrupted application of 3 total days (up to 72 hours). A photograph of the site where the study device was applied will also be taken on Day 3, following removal of the study device, and at each follow-up visit.

The SAR questionnaire will be administered by study staff immediately following application of the study device to assess tolerance, side effects, and/or adverse reactions (App. A). For the purposes of this study, if 2 subjects experience an unacceptable adverse reaction warranting discontinuation of treatment in the opinion of the Investigators during the initial phase of the study, the study will be halted and the second phase (and the remainder of the initial phase, if applicable) will not be completed.. Allergic reactions and infections at the device application site will be considered unacceptable at any clinical severity; other adverse reactions will be deemed "unacceptable" by the Investigators on a case-by-case basis dependent upon clinical severity (App. A).

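### Section 9.0 compares categorical variables between visits with independent-sample tests, although the visits repeat the same 10 subjects per group (minor impact)

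*Combined protocol and SAP*

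**What the plan says.** Section 9.0 gives the rule for categorical data in one sentence: "Dichotomous and categorical variables will be reported as frequencies with percentages and compared between follow-up times using Chi-square tests or Kruskal Wallis tests". The sentence before it says that continuous variables will be "compared between baseline and follow-up times using paired t-tests and/ or repeated measures ANOVA". The paragraph opens with "Descriptive statistics will comprise the bulk of the statistical analysis" and sets p<0.05 for all the tests.

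The samples are described in Section 3.2. For Group 1, "Five (5) white subjects and 5 black or African American subjects will be enrolled to evaluate skin differences". For Group 2, "The subsequent wound care subject study will include 10 subjects".

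The visits are repeats of those subjects. Section 5.1 has Group 1 wear the device for three days, "followed by weekly visits for 4 weeks of observation for tolerance, side effects, and adverse reactions"; the follow-up days are 10, 17, 24 and 31. The SAR questionnaire is also given on Day 3 (Section 5.1) and on Day 0: "The SAR questionnaire will be administered by study staff immediately following application of the study device" (Section 5.7). Group 2 is seen through up to 3 months of treatment and then at 3, 6, 9 and 12 months.

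No section names a within-subject method for categorical variables, and Section 9.0 does not say which visits are compared.

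**The concern.** The Pearson Chi-square and Kruskal-Wallis tests refer their statistics to distributions derived for independent samples. Here the samples are the same people seen again, so the reference distribution is wrong. The plan handles this correctly for continuous variables and not for categorical ones. Reading the sentence as a comparison between subgroups, such as the two race groups, does not fit, because it says the comparison is between follow-up times.

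At stake is how any between-visit p-value for tolerance or skin reactions would be read. With a test whose true size is well below 5%, a non-significant result says less than its label suggests. The undefined visit set adds to this: for the SAR questionnaire in Group 1 it could be four, five or six visits.

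**Working it through.** **Inputs from the documents.** n = 10 per group (Section 3.2); k = 4 Group 1 follow-up visits (Sections 5.1 and 5.3); significance level 0.05 (Section 9.0). The plan states no power or size for these tests, so there is no figure to reproduce.

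**Assumed inputs.** A constant 40% reaction rate, and within-subject correlation on a latent-normal scale of 0.3, 0.5 or 0.7, either exchangeable or serial (AR(1)). The documents give neither quantity.

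**Step 1: direction, by formula.** With s_j reactions at visit j, mean s̄ over visits and overall proportion p̂, the Pearson statistic is X² = Σ(s_j − s̄)² / [n p̂(1 − p̂)], on k − 1 = 3 degrees of freedom, with 5% critical value 7.815. If the binary outcomes have exchangeable correlation ρ and a constant rate p, then E[Σ(s_j − s̄)²] = (k − 1) n p(1 − p)(1 − ρ). So X² behaves roughly as (1 − ρ) times a chi-square on 3 df, and the true size is about P(χ²₃ > 7.815/(1 − ρ)). Any positive ρ shrinks the statistic.

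At a 40% rate, latent correlation 0.3 / 0.5 / 0.7 corresponds to ρ = 0.191 / 0.330 / 0.490:

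- 7.815/0.809 = 9.66, tail 2.2%
- 7.815/0.670 = 11.66, tail 0.9%
- 7.815/0.510 = 15.32, tail 0.2%

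**Step 2: size, by simulation at n = 10.** True size at nominal 5%, four visits, constant 40%:

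| Latent correlation | 0 | 0.3 | 0.5 | 0.7 |
|---|---|---|---|---|
| Exchangeable | 4.7% | 2.2% | 1.0% | 0.3% |
| Serial | – | 3.2% | 2.1% | 0.9% |

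This agrees with Step 1, and repeat simulations agreed to within 0.2 points. Kruskal-Wallis behaves alike: with an assumed four-level score its size is 1.9 / 0.9 / 0.2% exchangeable and 2.3 / 1.8 / 0.5% serial. The effect fades over long series with serial correlation. At 17 visits, serial 0.5 and a 50% rate, the sizes are 4.0% (Chi-square) and 4.4% (Kruskal-Wallis).

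**Step 3: would a matched test find more?** Power of Chi-square against Cochran's Q with a permutation p-value, n = 10:

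| Assumed rates by visit | Correlation settings | Chi-square | Permutation Q |
|---|---|---|---|
| 40/20/10/10% | exchangeable 0 / 0.3 / 0.5 / 0.7 | 31 / 27 / 25 / 24% | 24 / 27 / 28 / 31% |
| 70/57/43/30% | exchangeable 0 / 0.3 / 0.5 / 0.7 | 31 / 27 / 23 / 20% | 26 / 31 / 34 / 41% |
| 40/20/10% | range over exchangeable and serial | 20–27% | 17–19% |
| 20/10/5/5% | range over exchangeable and serial | 6–11% | 4–7% |

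For two visits (70% versus 30%, exchangeable 0 to 0.7), uncorrected Chi-square has 39–42% power, mid-p McNemar 33–37% and exact McNemar 18–20%. The sign of the difference depends on the assumed pattern.

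**Step 4: what an interval would show.** Exact 95% limits: 0/10 gives an upper limit of 1 − 0.025^(1/10) = 0.308, so 0–31%; 3/10 gives 7–65%.

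**The case against.** The strongest case on the other side is that nothing depends on these tests. The analysis is mainly descriptive. The primary endpoint is a continuous percent change in area (Section 2.2), the secondary endpoint is a single proportion (Section 2.4), and the Group 1 halting rule is a count of two subjects (Sections 2.1 and 3.3). No section names a categorical outcome to be compared between visits. The SAR questionnaire is the likely candidate, but its response scale is in Appendix A, which is not in the text reviewed. All of this stands, and it limits the point to a minor one. It does not make the stated tests suitable for repeated observations.

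Three stronger readings are tempting and are not supported:

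- **Too many false positives.** With positive within-subject correlation the error runs the other way, and no positively correlated scenario examined put Chi-square or Kruskal-Wallis above 5%. The conservatism is itself conditional on that correlation.
- **A real change in skin reactions will be missed, and a matched test would find it.** The largest gain found, 17.2% to 44.5% (27 points), needs a steady 70% to 30% fall over five visits at exchangeable correlation 0.7. Section 7.1.1 expects symptoms within 24–72 hours and resolution within 7–10 days of removal, though possibly 30 days or more. That is closer to early resolution. For an assumed 70/40/20/10/10% pattern both tests do well (79–82% for Chi-square, 80–94% for permutation Q), and for rarer reactions the matched test is mostly lower.
- **The study's conclusions or its halting decision are compromised.** None of them uses these p-values.

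Matched tests also have a cost in Group 2. Under Section 5.11 a subject whose ulcer heals stops treatment, so a complete-block test that includes later treatment visits would drop the early healers. The general sentence on imputation in Section 9.0 does not say how this would be handled.

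**Conclusion.** The point holds as a mismatch between test and design. Section 9.0 names independent-sample tests for repeated observations of the same 10 subjects per group, so their p-values are not valid as written. The mismatch follows from the text alone. Its size does not: the figures of about 0.3–3.2% true size against a nominal 5% rest on an assumed 40% rate, four visits and positive correlation of 0.3 to 0.7. At zero correlation the size is close to nominal. The impact is minor, and the case for changing the sentence is validity and clarity, not recovery of power.

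**What to change.** Replace the sentence on dichotomous and categorical variables in Section 9.0 with:

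> Dichotomous and categorical variables will be reported at each visit as frequencies and percentages with the number of subjects contributing, with exact 95% confidence intervals for dichotomous outcomes. No tests between visits will be done.

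This fits the descriptive plan, and the width of the intervals shows how little 10 subjects can say. The contributing number matters in Group 2 because subjects leave at different times for reasons tied to healing.

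If a between-visit test is kept, the plan should:

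- use a within-subject test, for example McNemar or permutation Cochran's Q for dichotomous outcomes, and Wilcoxon signed-rank or Friedman for ordinal ones;
- name the visit set before analysis, including whether Group 1 means the four follow-up visits only or also Day 3 or Day 0;
- state how subjects who leave treatment early because they healed are handled;
- give validity as the reason for the choice, not a gain in power.

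The cost is one short paragraph, with no new data and no change to visits or treatment. The main option gives up between-visit p-values, on which nothing rests. Keeping tests adds a little work, and the effect on power could go either way.

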8.2.2 Objectives

The main objectives of the Monitoring Plan are to:

- ♦ Ensure that the rights and well-being of human subjects are protected.
- ♦ Ensure that key reported trial data are accurate, complete, and verifiable from source documentation.
- ♦ Assure the study site is familiar with and follows the protocol.
- ♦ Assure the site is GCP compliant and compliant with applicable regulatory requirements.

"Safety and Efficacy of the Noxsano Wound Care Bandage: A First-in Human Study" is designed to determine the safety and effectiveness of the Noxsano device. The initial safety assessment will be conducted in healthy volunteers as part of an IRB-approved study. Once safety has been established, the efficacy and safety of the Noxsano device will be evaluated in subjects with an active wound as part of an IRB-approved study.

IRB# 1331496 Page 38 Version 6.0

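### Section 9.0 defines no safety measure for Group 1's primary safety objective, and its only comparison for categorical data, between follow-up times, does not estimate how many subjects react

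*Combined protocol and SAP*

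**What the plan says.** Sections 2.1 and 9.0 make safety in healthy volunteers the primary objective for Group 1. The only primary endpoint, in Sections 2.2 and 9.0, is the change in wound area in Group 2.

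For analysis, Section 9.0 says "Descriptive statistics will comprise the bulk of the statistical analysis". For categorical data it says "Dichotomous and categorical variables will be reported as frequencies with percentages and compared between follow-up times", with Chi-square or Kruskal-Wallis as the tests. It names no safety variable, no denominator, no confidence interval and no summary by skin group.

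Section 3.2 fixes the sizes. For Group 1, "Five (5) white subjects and 5 black or African American subjects will be enrolled to evaluate skin differences". For Group 2, "The subsequent wound care subject study will include 10 subjects from the patient population".

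The decision to go on to Group 2 is described in two ways. Sections 2.1 and 9.0 let Group 2 proceed if Group 1 shows no issues of tolerance, side effects or adverse reactions. Sections 2.1, 3.3 and 5.7 halt the study once two subjects have an unacceptable reaction in the initial phase. Section 8.2.2 then says "Once safety has been established, the efficacy and safety of the Noxsano device will be evaluated" in subjects with an active wound.

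**The concern.** The safety question in a first-in-human group is how many people react, how severely, and how high a rate the data leave open. Section 9.0 specifies no analysis for this. The one comparison it does specify asks whether the frequency of a reaction differs between visits. A stable low frequency and a stable high frequency both give a non-significant result, and the tests named assume independent observations although every visit involves the same subjects.

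In Group 2 the visit denominator is a further problem. Section 5.11 removes subjects with an allergic reaction or site infection from study treatment, and ends study follow-up for those whose wounds do not respond. Percentages at later visits can then be calculated without the people who reacted.

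At stake is the safety statement in the report. It could rest on low visit percentages and non-significant tests, with no count of people affected and no limit on the rate.

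**Working it through.** The documents give no precision, reaction rate or interval for safety, so there is no planned figure to reproduce. The checks below use the sample sizes and visit schedule. The two-sided 95% level is my assumption; Section 9.0 gives only p<0.05 for tests.

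**Inputs**
- Group 1: n = 10, with 5 per skin group (Section 3.2). Group 2: n = 10.
- SAR questionnaire in Group 1: Days 0, 3, 10, 17, 24 and 31, so 6 times (Section 5.1).
- SAR questionnaire in Group 2: Day 0, twice weekly for up to 4 weeks, weekly in weeks 5 to 12, then at 3, 6, 9 and 12 months. At most 1 + 8 + 8 + 4 = 21 times.
- Halting rule: two subjects with an unacceptable reaction (Sections 2.1, 3.3, 5.7).

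**1. What the between-visit comparison measures (assumed example).** Let 4 of 10 volunteers react, each at one visit only. The proportion who ever reacted is 4/10 = 40%, exact 95% CI 12.2% to 73.8%.

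| Timing | Highest visit frequency | Chi-square over 6 visits (5 df) |
|---|---|---|
| Four different visits | 1/10 = 10% | 2.14, p = 0.83 |
| All at Day 3 | 4/10 = 40% | 21.43, p = 0.0007 |

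For the second row, each visit has an expected 4/6 = 0.667 reactors and 9.333 non-reactors. The reactor cells give (4 − 0.667)²/0.667 + 5 × 0.667 = 20.00. The non-reactor cells give (6 − 9.333)²/9.333 + 5 × 0.667²/9.333 = 1.43. The sum is 21.43. Both p-values are nominal, because the test wrongly treats 60 observations on 10 people as independent. The number of people who react is the same in both rows, so the comparison responds to timing and not to that number.

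**2. Group 2 denominators (assumed example).** If 2 of 10 subjects have a site infection, are removed from treatment and provide no further questionnaires, later visits show 0/8 = 0%. The proportion who ever reacted is 2/10 = 20%, exact 95% CI 2.5% to 55.6%.

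**3. What a correct count can exclude.** With no events in n subjects, the Clopper-Pearson upper limit is 1 − 0.025^(1/n). With one event in 10, it solves (1 − p)^10 + 10p(1 − p)^9 = 0.025.
- 0/10: 1 − 0.025^(1/10) = 30.8%
- 1/10: 44.5% (check: 0.0028 + 0.0222 = 0.025)
- 0/5, one skin group: 1 − 0.025^(1/5) = 52.2%
- One-sided 95% limits for 0/10 and 1/10 are 25.9% and 39.4%; Wilson limits are 27.8% and 40.4%.

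**4. The halting rule taken alone.** The chance of not halting is (1 − p)^10 + 10p(1 − p)^9, where p is the true rate of unacceptable reactions.
- p = 10%: 0.349 + 0.387 = 74%
- p = 20%: 0.107 + 0.268 = 38%
- p = 30%: 0.028 + 0.121 = 15%

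These figures describe the two-subject rule only. They do not describe the other statement, under which any issue counts.

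**5. Skin groups.** Reactions in 2/5 against 0/5 give a two-sided Fisher p of 0.44. A test between groups of 5 would tell the reader little, so a descriptive summary is what the design supports.

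**The case against.** A reader might infer that the decision to open Group 2 rests on an under-count. The documents do not support that. The halting rule counts subjects over the whole initial phase, and Section 3.2 requires Group 1 follow-up to be complete and the results assessed first. Volunteers who react at different visits are added together for that rule, and it does not use the percentages in Section 9.0.

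A reader might also attribute the 31% and 45% limits to under-counting. They are limits for a correctly counted 0 or 1 in 10 and come from the sample size. Tied to the halting rule, they concern unacceptable reactions. Milder reactions are not held to 0 or 1 by that rule, so their upper limit could be higher.

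Three more points stand in part. Frequencies with percentages do not exclude an overall count per subject; only the comparison is tied to visits. Section 7.1.1 expects onset within 24 to 72 hours of application, which would concentrate reactions at Day 3 and make any Group 1 under-count small. The wording of the SAR questionnaire (Appendix A) is not in the text available, so whether it asks about current symptoms or symptoms since the last visit cannot be checked.

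It can also be said that Section 8.2.2 is monitoring-plan narrative and that its sentence continues safety evaluation in Group 2. That softens the word established but does not justify it. On skin groups, Section 3.2 promises no test, and none is asked for here.

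None of this supplies a safety measure for a primary objective or makes the between-visit comparison suitable.

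**Conclusion.** The point holds in a limited form and should be acted on. Section 9.0 specifies no estimate of how many subjects react. The comparison it does specify answers another question with tests that ignore repeated measurement, and in Group 2 visit percentages can lose subjects who reacted. In the assumed Group 1 example, a true 40% appears as a highest visit frequency of anywhere from 10% to 40%. The lower end needs reactions spread over visits, which the expected time course makes less likely. The Group 2 loss assumes that removed subjects give no further questionnaires; the documents do not settle this.

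Separately, 10 volunteers leave rates of up to 31% (0/10) or 45% (1/10) not excluded, on two-sided exact 95% limits. That is too wide to describe safety as established.

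The two statements of when Group 2 may proceed also disagree: one volunteer with an unacceptable reaction is an issue under one and does not trigger a halt under the other. They must be reconciled; which should apply is not a statistical matter for this review.

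**What to change.** In Section 9.0:
- Define the safety measure as the number and percentage of subjects with at least one event from first application to last visit, over all subjects with a device applied.
- Report it for any reaction, for each SAR item and for unacceptable reactions.
- Give exact (Clopper-Pearson) 95% limits for Group 1 overall, descriptively by skin group, and for Group 2.
- Drop the between-visit tests for SAR items. Visit tables can remain as description of time course, with the number assessed shown at each visit.
- State with the Group 1 conclusion the rate that the observed count does not exclude.

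Elsewhere, replace the wording in Section 8.2.2 that treats safety as established with wording that matches the reconciled gate, and reconcile the two gate statements across Sections 2.1, 3.3, 5.7 and 9.0.

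The data are already collected: SAR responses at the scheduled visits, and all adverse events after consent (Section 7.3). The cost is wording and a few tables, with no new visits or subjects. The safety statement will read less favourably.
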